9.1 Adverse Events Definition

An **adverse event** (AE) is any symptom, sign, illness or experience that develops or worsens in severity during the study that does not necessarily have a causal relationship with this treatment. Intercurrent illnesses or injuries should be regarded as adverse events. Abnormal results of diagnostic procedures are considered to be adverse events if the abnormality:

- results in study withdrawal
- is associated with a serious adverse event
- is associated with clinical signs or symptoms
- leads to additional treatment or to further diagnostic tests or considered by the investigator to be of clinical significance

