9.4 Adverse Events Assessment and Recording

At each contact with the participant, the investigator or study staff will assess for information on adverse events and review all self-reported AE's via the study portal. Information surrounding adverse events should be recorded in the study portal. Related signs, symptoms, and abnormal diagnostic procedures results should be recorded in the study portal and grouped under one diagnosis as applicable.

Adverse events can be spontaneously reported or elicited during open-ended questioning. Adverse events will be measured and graded in accordance with the document entitled *Division of AIDS (DAIDs) Table for Grading the Severity of Adult and Pediatric Adverse Events, Corrected Version 2.1, July 2017* issued by the US Department of Health and Human Services. The clinical course of each event should be followed until resolution, stabilization, or until it has been determined that the study treatment or participation is not the cause. Serious adverse events that are still ongoing at the end of the study period must be followed up to determine the final outcome. Any serious adverse event that occurs after the study period and considered to be at least possibly related to the study treatment or study participation should be recorded and reported immediately.

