9.4.1 Relationship to Study Drug

The causal relationship can be one of the following:

- Related: There is a possible, probable or definite causal relationship between study drug administration and the AE
- Not related: There is evidence suggesting a causal relationship to something other than the study drug.

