10.1 Important Medical Event

Important medical events are those that may not be immediately life threatening but are clearly of major clinical significance. They may jeopardize the participant and may require intervention to prevent one of the other serious outcomes noted above. For example, drug overdose or abuse, a seizure that did not result in in-patient hospitalization, or intensive treatment of bronchospasm in an emergency department would typically be considered serious.

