 - Safety monitoring indicates that a particular side effect is more severe, or more frequent than initially expected.

PATCH 2 & 3 TRIAL

-- A paper is published from another study that shows that an arm of your research study is of no therapeutic value.

- Change in FDA safety labeling or withdrawal from marketing of a drug, device, or biologic used in a research protocol.
- Breach of confidentiality
- Change to the protocol taken without prior IRB review to eliminate apparent immediate hazard to a research participant.
- Incarceration of a participant when the research was not previously approved under Subpart C and the investigator believes it is in the best interest of the participant to remain on the study.
- Complaint of a participant when the complaint indicates unexpected risks, or the complaint cannot be resolved by the research team.
- Protocol violation (meaning an accidental or unintentional deviation from the IRB approved protocol) that in the opinion of the investigator placed one or more participants at increased risk or affects the rights or welfare of participants.

The IRB will accept other reports when the investigator is unsure whether the event should be reported, and the IRB will review such reports to determine whether the event meets the threshold for an unanticipated event presenting risk to the participant. Reports requiring IRB consideration or consultation are to be emailed to [name], Vice President, Human Research Affairs at UnitedHealth Group at [contact].

11.1 Reporting Process to IRB.

Principal Investigators are encouraged to submit reports of unanticipated problems posing risks to participants or others via a written report of the event (including a description of the event with information regarding its fulfillment of the above criteria, follow-up/resolution and need for revision to consent form and/or other study documentation) within 7 working days to the UnitedHealth Group Office of Human Research Affairs (OHRA). Participating sites should follow local, institutional guidelines on Event Reporting. For reportable deaths, the initial submission to the IRB may be made by contacting [name] at [contact].

This study is IND exempt and reporting to the FDA is voluntary using a MedWatch 3500 or via the FDA's website for voluntary reporting.

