PATCH 3 (Sub-Study 2), Prophylaxis in Health Care Workers: The transmission of SARS-COV-2 from patient to hospital worker depends on many factors including specifics of standard care to prevent transmission, but especially on the number of patients seen at a given hospital or outpatient practice. Across China the reported hospital worker infection rate is 3.8%, but in Wuhan it is reported as 58% at the height of the epidemic. We will use a 10% transmission rate as the null hypothesis (low dose group). In order for HCQ to be considered effective our alternative hypothesis will be a 1% transmission rate. With a 1:1 randomization for the HCQ to control arms we would require a total of 350 health care workers across all participating ProHealth NY and AHN sites. With the placebo group of 175 participants and the high dose HCQ arm of 175 participants, a one-sided z-test ($\alpha=0.05$) comparing the rates in the two groups would have an at least 80% power to detect a significant difference when the difference in the population rates is at least 9%.

The *hypothesis* will be tested using a one-sided test, with a z-score corresponds to the log of the odds-ratio for the rate of transmission between the two groups. We will obtain the estimate of the odds ratio, and 95% CI, from logistic regression.

Interim analysis: We will perform two interim analyses at 25% and 50% completion, testing for early efficacy or futility, using z-score boundaries that follow Hwang-Shih-DeCani alpha spending rules. Following those rules, we have 80% power using 100% of the sample, if our 10% versus 1% scenario is true.

Z-Value Boundaries

Stage	Boundaries		Information Proportion
	Efficacy	Futility	
1	2.9473	-1.2318	0.2500
2	2.5825	-0.2676	0.5000
3	1.6664	1.6664	1.0000

P-Value Boundaries

Stage	Boundaries		Information Proportion
	Efficacy	Futility	
1	0.00160	0.89099	0.2500
2	0.00491	0.60550	0.5000
3	0.04782	0.04782	1.0000

16.2 Analysis of Secondary Endpoints.

Secondary outcomes will be analyzed as summary statistics, with group means, odds-ratios, and 95% CIs. We may conduct exploratory analyses using regression methods appropriate for each type of measure. Tests for significance of estimated parameters will not be reported as we will not be controlling for multiple testing.

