PATCH 2 (Sub-Study 1): Rate of secondary infection of housemates is a binomial count by household. We will summarize the proportion or rate by group, with 95% CI. With sufficient data, we will explore subgroups, patient, and secondary patient characteristics using logistic regression. Rate of hospitalization is a binary measure. We will summarize rates by group and estimate the odds-ratio for treatment. Adverse event rates will be summarized as a count by participant, and mean count by group, and we will estimate a rate-ratio for treatment. We will summarize rates by group and estimate the odds-ratio for treatment.

PATCH 3 (Sub-Study 2): Rate of hospitalization is a binary measure. We will summarize rates by group and estimate the odds-ratio for treatment. Adverse event rates will be summarized as a count by participant, and mean count by group, and we will estimate a rate-ratio for treatment. We will summarize the count of shifts missed by group and estimate the rate ratio for treatment.

REFERENCES

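### Section 16.2's only explicit adverse-event analysis counts every event alike; apart from hospitalization, no by-arm comparison of serious, Grade 3+ or related events is specified

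*Combined protocol and SAP*

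**What the plan says.** The rate of adverse events is a secondary objective of both sub-studies (section 1.2). Section 16.2 uses the same sentence for each: "Adverse event rates will be summarized as a count by participant, and mean count by group, and we will estimate a rate-ratio for treatment". It sets no restriction by grade, seriousness or relatedness. Section 9.1 defines an adverse event as "any symptom, sign, illness or experience that develops or worsens in severity during the study", with no causal link required, so the count is broad.

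Two other sentences in 16.2 might bear on this. In the PATCH 2 paragraph, the adverse-event sentence is followed by "We will summarize rates by group and estimate the odds-ratio for treatment", with no outcome named. The opening of 16.2 adds "We may conduct exploratory analyses using regression methods appropriate for each type of measure", which is optional and names no adverse-event measure.

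The information needed for a finer comparison is collected:
- Severity (9.4): "Adverse events will be measured and graded in accordance with the document entitled" the DAIDS table.
- Relatedness (9.4.1): an event is related if "There is a possible, probable or definite causal relationship between study drug administration and the AE".
- Seriousness (10.0): all SAEs after consent are collected, related or not.

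**The concern.** A count that gives each event the same weight is driven by the commonest events. The side-effect guides in Appendices 3 and 4 list nausea, stomach pain and stomach cramps at 10% or more each on HCQ, and say the frequency of the serious effects cannot be estimated. A rate ratio above 1 could therefore reflect nausea, and a ratio near 1 could hide a difference in serious events. The specified result does not let a reader tell which.

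This matters most in PATCH 3, where asymptomatic health care workers take 600 mg daily for up to 60 days and section 9.5 requires no safety laboratory tests. What is at stake is the safety account. The efficacy analyses do not depend on it.

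**Working it through.** **Does another part of the plan fill the gap?**
- *The unattributed odds-ratio sentence (PATCH 2).* It may belong to COVID-19 negativity, a secondary objective that 16.2 otherwise leaves out. Even read as any adverse event, it ignores severity. PATCH 3 has no such sentence after its adverse-event line.
- *Safety monitoring.* Grade 3+ events lead to drug being withheld (8.5). An independent clinician reviews the number and type of SAEs (13.0), and the team reviews them weekly (13.1). Section 11.0 makes it reportable to the IRB if "Safety monitoring indicates that a particular side effect is more severe, or more frequent than initially expected". None of these states a comparison between arms.
- *Hospitalization.* It is compared by arm in both sub-studies and is the nearest substitute. It misses serious events without admission, of which 10.1 gives examples: "a seizure that did not result in in-patient hospitalization, or intensive treatment of bronchospasm in an emergency department would typically be considered serious". It also mixes drug harm with COVID-19 admissions, which 10.2 generally keeps out of adverse-event reporting.

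**Can the all-event ratio show a serious excess?** The plan has no figure to reproduce here. The one input it gives is n = 175 per arm in PATCH 3 (16.1). The rest are assumptions, shown as ranges: m = 1, 2 or 4 events per placebo participant; s = serious excess per HCQ participant; g = mild excess per HCQ participant.

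RR = (m + s + g) / m

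SE(log RR) = √[1/(n·m) + 1/(n·(m + s + g))]

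P(lower 95% limit > 1) = Φ(log RR / SE − 1.96)

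Worked case, m = 2, s = 0.05, g = 0: RR = 2.05/2 = 1.025; SE = √(1/350 + 1/358.75) = 0.0751; 95% CI 0.89 to 1.19; P = Φ(0.0247/0.0751 − 1.96) = 0.051.

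| Excess on HCQ | RR at m = 1 / 2 / 4 | P(lower limit > 1) |
|---|---|---|
| Serious 0.02 only | 1.02 / 1.01 / 1.005 | 0.038 / 0.034 / 0.031 |
| Serious 0.05 only | 1.05 / 1.025 / 1.01 | 0.067 / 0.051 / 0.042 |
| Mild 0.1 only | 1.10 / 1.05 / 1.025 | 0.147 / 0.096 / 0.067 |
| Mild 0.3 only | 1.30 / 1.15 / 1.075 | 0.742 / 0.481 / 0.280 |
| Mild 0.3 + serious 0.05 | 1.35 / 1.175 / 1.09 | 0.853 / 0.602 / 0.360 |

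A serious excess of 5 per 100 adds 0.05/m to the ratio, which is 0.05, 0.025 or 0.0125. With no true difference, the last column would be 0.025. With extra-Poisson variation (variance μ + 0.5μ²), the serious-only 0.05 row falls to 0.034–0.057.

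**PATCH 2 size.** With 250 per arm, 2 non-serious events per participant, and SAE rates of 1% and 5%, RR = 2.05/2.01 = 1.02 (95% CI 0.90 to 1.15).

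**Direction can reverse.** If mild events fall from 2.0 to 1.8 per participant while SAEs rise from 1% to 5%, RR = 1.85/2.01 = 0.92.

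**Matched pair (n = 175, 403 vs 350 events).** RR = 403/350 = 1.15; SE = √(1/403 + 1/350) = 0.0731; 95% CI 0.998 to 1.33. Two different trials give this same result:
- Trial A has 53 extra mild events, and SAE participants are 2 vs 2. The SAE risk difference is 0.0 points (exact 95% CI −3.1 to 3.1).
- Trial B has 45 extra mild and 8 extra serious events, and SAE participants are 10 vs 2. The difference is 8/175 = 4.6 points (0.8 to 9.3).

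**Limits of the SAE line.** A split of 5 vs 2 participants gives 3/175 = 1.7 points (−1.6 to 5.6). Power of a one-sided 2.5% Fisher test is 13% at 3% vs 1%, and 7% at 2% vs 0.5%.

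**The case against.** A reader might infer that the plan gives no by-arm view of serious harm at all. It does give one: needing or prolonging a hospital stay is an SAE criterion (10.0), and hospitalization is compared by arm in both sub-studies. That narrows the gap to SAEs without admission, Grade 3+ events, related events, and the separation of drug-related from COVID-19 admissions.

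A reader might also infer that data capture is incomplete, because 8.4 mentions completing grading if necessary and 9.2 ends adverse-event reporting at the last dose. The documents do not support this. Section 9.4 says events will be graded. Section 8.4 requires follow-up in PATCH 3 when an event cannot be graded from portal data. Section 10.0 collects all SAEs after consent without a clear last-dose cutoff. The gap is in the specified analysis.

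The magnitude uses chosen scenarios. Section 2.3 reports no retinal, cardiac, neurological, hepatic or renal toxicity in over 220 cancer patients, and people at raised cardiovascular risk are excluded. A serious excess of 5 per 100 may be too large. A smaller excess, however, would be still less visible in the all-event ratio, and the SAE line would be imprecise too.

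Finally, 16.2 is descriptive throughout, and nothing prevents the sponsor from producing these tables later. That is true, but nothing commits the sponsor to them either.

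**Conclusion.** The point holds in this limited form. The one explicit adverse-event analysis cannot separate serious from mild events. Outside hospitalization, no by-arm comparison of serious, Grade 3+ or related events is specified. Under the assumed rates (175 per arm, 1 to 4 events per placebo participant, Poisson counts), a serious excess of 5 per 100 shifts the ratio by 0.01 to 0.05. Its lower limit then exceeds 1 in 4–7% of trials, against 7–74% for a purely mild excess of 0.1 to 0.3 events per participant. Exact values depend on event rates that the plan does not give. That every event counts equally follows from the text alone.

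Two stronger readings do not follow. No efficacy conclusion is affected, and adding SAE proportions would not create a powered safety test. The gain is visibility. The change should be made because it is cheap and uses data already collected.

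**What to change.** Add to 16.2, for both sub-studies and for participants who took at least one dose, by arm as randomised:
- Number and percent with at least one SAE, at least one Grade 3+ AE and at least one related AE, with risk differences, exact 95% confidence intervals and no significance tests.
- A listing of SAEs by arm in reported terms, since no event coding is described.
- The all-event rate ratio, kept as a supporting line.

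*PATCH 2.* Section 16.1 expects about 100 of 500 to test positive, so about 400 would be told to stop drug (section 4.0, step 7). An all-dosed table alone would dilute any contrast. Show it for all dosed and separately for test-positive participants, with exposure days by arm. Because of 10.2, state whether COVID-19 admissions are counted in the SAE line.

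*PATCH 3.* Keep the table as randomised and flag events on open-label HCQ after crossover.

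Use SAE data as already collected under section 10.0, with follow-up days shown by arm. No added Day-60 contact is needed.

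The cost is SAP wording and a few more descriptive tables, with no new patients. The downside is low precision, as the 5 vs 2 example shows, so the tables should be labelled descriptive.

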Appendix 1: PATCH 2 Process Flows

PATCH2 STUDY: Patients (500 Participants)

[figure not shown]
Randomized trial of hydroxychloroquine in the treatment of COVID-19
 High-Level Patient Journey Map

PATCH 2 & 3 TRIAL

[figure not shown]
PATCH2 STUDY: Patients (500 Participants)

Awareness & Identification Randomized trial of hydroxychloroquine in the prevention and treatment of COVID-19

PATCH2 STUDY: Patients (500 Participants)

[figure not shown]
Enrollment Channels Randomized trial of hydroxychloroquine in the treatment of COVID-19

PATCH 2 & 3 TRIAL

[figure not shown]
PATCH2 STUDY: Patients (500 Participants)

Enrollment Randomized trial of hydroxychloroquine in the treatment of COVID-19

PATCH2 STUDY: Patients (500 Participants)

Randomization & Study ID Process

PATCH2 STUDY: Patients (500 Participants)

[figure not shown]
Medication & study kit determinations

PATCH2 STUDY: PATIENT POPULATION 500 Participants	
PARTICIPANT PACKAGE 1: Blinded Label PATIENT + ACTIVE MEDICATION (A total of 250 shipments)
 
 Pill Bottle containing 200mg pills (56 count) Instructions: (Take 400mg (2 pills) in the AM daily and 400mg (2 pills) in the PM- 12 hours apart- for 14 days. no refill) Patient Thermometer (as available) Study ID Card Study Journal/ Instructions/ FAQ/ Side effect & Contact information 	
PARTICIPANT PACKAGE 1: Blinded Label PATIENT + PLACEBO (A total of 250 shipments)
 
 Pill Bottle containing 200mg placebo pills (56 count) Instructions: (Take 400mg (2 pills) in the AM daily and 400mg (2 pills) in the PM- 12 hours apart- for 14 days. no refill) Patient Thermometer (as available) Study ID Card Study Journal/ Instructions/ FAQ/ Side effect & Contact information
---	--	--

PATCH 2 & 3 TRIAL

PATCH2 STUDY: Patients (500 Participants)

[figure not shown]
Participation Randomized trial of hydroxychloroquine in the treatment of COVID-19

PATCH 2 & 3 TRIAL

PATCH2 STUDY: Patients (500 Participants)

[figure not shown]
[figure not shown]
Symptoms/ Adverse Events Randomized trial of hydroxychloroquine in the treatment of COVID-19

Appendix 2: PATCH 3 Process Flow

[figure not shown]
PATCH3 STUDY: HEALTH CARE WORKERS (350 Participants)

Randomized trial of hydroxychloroquine in the prevention of COVID-19
Health Care Worker (HCW) Journey Map

PATCH3 STUDY: HEALTH CARE WORKERS (350 Participants)

[figure not shown]
Study Awareness Randomized trial of hydroxychloroquine in the prevention of COVID-19

PATCH 2 & 3 TRIAL

[figure not shown]
PATCH3 STUDY: HEALTH CARE WORKERS (350 Participants)

Enrollment Randomized trial of hydroxychloroquine in the prevention of COVID-19

PATCH3 STUDY: HEALTH CARE WORKERS (350 Participants)

[figure not shown]
Randomization & Study ID Process (Offline- not consumer facing)

PATCH 2 & 3 TRIAL

[figure not shown]
PATCH3 STUDY: HEALTH CARE WORKERS (350 Participants)

Medication & study kit determinations Randomized trial of hydroxychloroquine in the prevention of COVID-19

PATCH3 STUDY: HEALTH CARE WORKERS (350 Participants)

[figure not shown]
Participation Randomized trial of hydroxychloroquine in the prevention of COVID-19

PATCH 2 & 3 TRIAL

PATCH3 STUDY: HEALTH CARE WORKERS (350 Participants)

[figure not shown]
Participation Randomized trial of hydroxychloroquine in the prevention of COVID-19

PATCH 2 & 3 TRIAL

PATCH3 STUDY: HEALTH CARE WORKERS (350 Participants)

[figure not shown]
Symptoms and/or Adverse Events Randomized trial of hydroxychloroquine in the prevention of COVID-19

PATCH 2 & 3 TRIAL

PATCH3 STUDY: HEALTH CARE WORKERS (350 Participants)

Cross-over Flow Randomized trial of hydroxychloroquine in the prevention of COVID-19

Appendix 3: PATCH 2 Job Aid

PATCH2 STUDY LEAD JOB AID

A PATCH2 AUTOMATIC STUDY EXCLUSIONS	
Consumer Language for Enrollment Exclusions 
 These exclusions are automatic during the online enrollment experience in the enrollment portal If indicated exclusion response is selected, it is an automatic exclusion from the study 	Automatic Portal Exclusion
Are you between the ages of 50-75? [yes/ no]	If NO
Have you had a fever within the last four days? [yes/ no]	If NO
Do you require hospitalization? [yes/ no]	If YES
Are you able to self-quarantine at home for 14 days? [yes/ no]	If NO
Have you been tested for COVID-19? [yes/ no]	If NO

B AUTOMATIC CLINICAL EXCLUSIONS		
Consumer Language for Enrollment Exclusions 
 These exclusions are automatic during the online enrollment experience in the enrollment portal If “yes” to any, it is an automatic exclusion from the study. 	Automatic Portal Exclusion	
Protocol Language: Allergy to hydroxychloroquine, 4 aminoquinolines, or quinine	Do you have an allergy to hydroxychloroquine (HCQ), aminoquinolines, or quinine? [yes/ no]	X
Protocol Language: Patients with G6PD deficiency	Do you have a G6PD deficiency? [yes/ no]	X
Protocol Language: Pregnant or lactating or positive pregnancy test during pre-medication examination	Are you pregnant? [yes/ no]	X
	Are you breast feeding? [yes/ no]	X
Protocol Language: Receiving any trial treatment drug for 2019-ncov within 14 days prior to screening evaluation (off label, compassionate use or trial related)	Have you been in any other drug trial for COVID-19? [yes/ no]	X
Protocol Language: Patients with serious intercurrent illness that requires active infusional therapy, intense monitoring, or frequent dose adjustments for medication including but not limited to infectious disease, cancer, autoimmune disease, cardiovascular disease.	Are you on any IV or other serious medications, such as chemotherapy? [yes/ no]	X
Protocol Language: Patients who have undergone major abdominal, thoracic, spine or CNS surgery in the last 2 months, or plan to undergo surgery during study participation.	Have you had any surgery in the last two months? [yes/ no]	X
Protocol Language: Patients currently taking digoxin	Do you take the medication, digoxin or lanoxin? [yes/ no]	X
(From Medication Section)	Have you ever had a seizures? [yes/ no]	X
(From Medication Section)	Have you ever had a transplant? [yes/ no]	X

PATCH 2 & 3 TRIAL

Protocol Language: History or evidence of increased cardiovascular risk including any of the following:
 
 • Left ventricular ejection fraction (LVEF) < institutional lower limit of normal. Baseline echocardiogram is not required; • Current clinically significant uncontrolled arrhythmias. Exception: Subjects with controlled atrial fibrillation; • History of acute coronary syndromes (including myocardial infarction and unstable angina), coronary angioplasty, or stenting within 6 months prior to enrollment; • Current ≥ Class II congestive heart failure as defined by New York Heart Association. 	
Do you have any heart disease such as congestive heart failure, history of heart attack, angina, arrhythmias or atrial fibrillation (also called AFib)? [yes/ no]
	
X

---	---	-----------------

C STUDY LEAD DECIDED EXCLUSIONS

Consumer Language for Enrollment Exclusions
 
 • These exclusions will be asked prior to the consent call through the study enrollment portal. “Yes” response do not trigger an automatic exclusion. • “Yes” responses require a live conversation between the prospective participant and the study lead during live consent. • If a medical consult is needed, then the study lead will conduct a medical consult with study PIs. Track all medical consult language in the study portal. • Call the prospective study participant back with the final decision (yes or no) on enrollment. If he/she is eligible, then finish study consenting, and trigger tablet + journal shipment

DISEASE EXCLUSIONS

Protocol Language	Study Portal Language		

Eye Disease: Known retinal disease including but not limited to macular degeneration, retinal vein occlusion, visual field defect, diabetic retinopathy
	
Do you have eye disease? [yes/ no]
		
	
(if yes) Please describe. [open text]
		
	
INCLUDED IF:
	
MEDICAL CONSULTATION IF:
	
EXCLUSION IF:

	
Wears eye glasses
		
Any eye disease

Protocol Language	Study Portal Language		

Lung Disease: History of interstitial lung disease, severe emphysema or asthma, or chronic pneumonitis unrelated COVID-19.
	
Do you have lung disease, such as asthma or emphysema? [yes/ no]
		
	
(if yes) Please describe. [open text]
		
	
INCLUSION IF:
	
MEDICAL CONSULTATION IF:
	
EXCLUSION IF:

	
If moderate or controlled
	
If in question, then medical consult
	
If severe, then exclude

Protocol Language	Study Portal Language		

Porphyria and Psoriasis: Due to risk of disease exacerbation patients with porphyria or psoriasis are ineligible unless the disease is well-controlled, and they are under the care of a specialist for the disorder who agrees to monitor the patient for exacerbations.
	
Do you have porphyria? [yes/ no]
		
	
Do you have psoriasis? [yes/ no]
		
	
INCLUSION IF:
	
MEDICAL CONSULTATION IF:
	
EXCLUSION IF:

	
If moderate or controlled
	
If in question, then medical consult
	
If severe, then exclude

MEDICATION EXCLUSIONS

Study Portal Language	Please list all medications that you are currently taking [text fields- one per medication]
	
 The following medications are not allowed during the study. The sponsor must be notified if the participant receives any of these during the study. Participants must be instructed not to take any medications, including over the counter products, without first consulting with the investigator. IF a study participant sees another provider, they are instructed to bring their study journal to this provider visit. IN ADDITION, the participant should contact the study lead any time they seek medical treatment.
Drug Classes	Protocol Language
Anticonvulsant	
 (Exclude) Patients receiving cytochrome P450 enzyme-inducing anticonvulsant drugs (i.e. phenytoin, carbamazepine, Phenobarbital, primidone or oxcarbazepine) within 4 weeks of the start of the study treatment Acceptable drug alternatives include: Because HCQ has known effects on P450 enzymes, patients requiring anti-convulsants may be treated with any of the non-enzyme inducing anti-convulsants which include: felbamate, valproic acid, gabapentin, lamotrigine, tiagabine, topiramate, or levetiracetam. Due to the fact that both zonisamide and HCQ accumulate in red blood cells, zonisamide should be avoided if possible. All other concomitant medications are permitted.
Antiviral	
 (Exclude) Any investigational or off-label antiviral therapy (Include) Patients with HIV may participate (Include) Patients with herpes may participate
Cancer Treatments	
 (Exclude) Anyone receiving active cancer treatments. (Exclude) Any concurrent chemotherapy, radiotherapy (except radiotherapy as designated in this study or radiotherapy indicated for CNS metastasis) (Exclude) Immunotherapy, (Exclude) Biologic or hormonal therapy for cancer treatment, except as noted in the exclusion criteria. (Include) A Cancer survivor receiving no treatments may participate (Include) Concurrent use of hormones for non-cancer-related conditions (e.g. insulin for diabetes, hormone replacement therapy).
Immunosuppressive	
 (Exclude) Immunosuppressive medications, including, corticosteroids at doses exceeding 10mg/day of prednisone or equivalent, methotrexate, azathioprine, and TNF-alpha blockers. (Include) Use of immunosuppressive medication for the management of study treatment related AEs or in subjects with contrast allergies is acceptable. (Include) In addition, use of topical, inhaled and intranasal corticosteroids is permitted.
Live attenuated vaccines	
 (Exclude) If using live attenuated vaccines during the study through 180 days after the last dose of both drugs. Examples include: MMR, Zostavax, Polio, Varicella (Include) If using non-living vaccines. Examples include: Flu vaccine, Pneumonia vaccine
Insulin or antidiabetic drugs	
 Reduce dosage consideration. As HCQ may enhance the effects of a hypoglycemic treatment, a decrease in doses of insulin or antidiabetic drugs may be required.
Arrhythmogenic	
 Drugs that prolong QT intervals. HCQ can prolong the QT interval and should not be administered with other drugs that have the potential to induce cardiac arrhythmias. Also, there may be an increased risk of inducing ventricular arrhythmias if HCQ is used concomitantly with other arrhythmogenic drugs
Antiepileptics	
 Side effect. The activity of antiepileptic drugs might be impaired if co-administered with HCQ.

Cyclosporin

- **Side effect.** An increased plasma cyclosporin level was reported when cyclosporin and HCQ were co-administered

See **medication look up tool** for inclusion or exclusion guidance related to specific medications

PATCH Medication Look-Up Tool

